No subjects had clinically significant ECG abnormalities during treatment with SOF+RBV. No meaningful change in systolic function measured by ejection fraction was observed in either treatment cohort. In addition, no subject had a decrease in ejection fraction below 50%. The median (Q1, Q3) change in ejection fraction from baseline to Week 24 for Cohort 1 was 0.09% (-0.97, 2.70), and in Cohort 2 was -0.73% (-4.28, 1.08). As compared to baseline echocardiograms, there were overall no significant changes in fractional shortening, left ventricular end diastolic volume (LVEDV), or left ventricular internal dimension in diastole (LVIDD) at Week 12 or Week 24.

No notable changes from baseline in vital signs (systolic blood pressure, diastolic blood pressure, or pulse rate) were observed during the study.

1.2.3. Additional Non-Clinical Toxicology Information

In dogs, repeated administration of GS-9851 (the diastereomeric mixture of SOF and GS-491241) or SOF at exposures similar to those expected in ESRD patients may decrease erythropoiesis and lower the numbers of circulating red cells (reflected by the decrease in red blood cells, hemoglobin concentration, and/or hematocrit). In the 4- and 13-week studies in dogs, there were slightly lower average circulating red cell indices, and minimally decreased erythropoiesis (observed by bone marrow cytology) at 500 and \geq 100 mg/kg/day, respectively. However, in the 39-week dog study, while minimally decreased erythropoiesis was observed in a few dogs, there were no SOF-related effects on circulating red cell indices at 500 mg/kg/day. In mice and rats, SOF did not affect hematology parameters at any dose level; specifically, there were no effects in mice dosed up to 1000 mg/kg/day for up to 13 weeks or in rats dosed up to 500 mg/kg/day for up to 26 weeks. There were also no bone marrow cytology findings in rats dosed up to 26 weeks. In vitro, the diastereomeric mixture GS-9851 also showed low cytotoxicity to erythroid cell lines.

1.3. Rationale for This Study

The GS-US-337-4063 study is a Phase 2, open-label, multicenter study evaluating the efficacy and safety of treatment of LDV/SOF for 8, 12, or 24 weeks in subjects on dialysis for ESRD. Approximately 100 subjects will be enrolled.

LDV/SOF (Harvoni[®]) is approved in the US, EU, and other regions for the treatment of genotype 1, 3 (EU only), 4, 5, and 6 HCV infection. However, subjects with severe renal impairment were not eligible for the registration LDV/SOF clinical studies. There is therefore no dosing recommendation provided for HCV-infected subjects with severe renal impairment or those on dialysis in the prescribing information in the US, EU, and other regions.

There remains a medical need for highly effective treatment for HCV-infected subjects with ESRD on dialysis. Chronic HCV infection has a significant negative impact on morbidity and mortality in subjects on dialysis {[Fabrizi 2007](#)}. The Kidney Disease International Working Group (KDIGO) recommend that HCV infection be treated prior to kidney transplant as there is evidence that this leads to improved graft and patient outcomes {[Kidney Disease: Improving Global Outcomes 2008](#)}.

Although, some regions do have approved HCV treatment options for HCV-infected subjects with severe renal impairment including Viekira Pak[®] and ZepatierTM {[AbbVie Inc 2016](#), [Merck & Co Inc 2016](#)}, both regimens have limitations. The use of Viekira Pak[®] is limited since many populations require the addition of ribavirin for optimal efficacy and RBV-induced toxicities are exacerbated in subjects with renal impairment. In addition, the components of Viekira Pak[®] (ombitasvir, paritaprevir, ritonavir, and dasabuvir) have drug-drug interaction potential which adds increasing complexity to the management of subjects with severe renal

impairment who frequently have multiple comorbid conditions and concomitant medications. The use of Zepatier is limited by the requirement for baseline resistance testing for subjects with genotype 1a infection and addition of RBV is required for some populations. Furthermore, both regimens carry the risk of alanine aminotransferase (ALT) elevations and/or hepatotoxicity and neither regimen is pangenotypic.

SOF-based regimens are currently the most widely prescribed treatments for HCV infection. Despite the lack of dosing recommendations for subjects with severe renal impairment in the prescribing information for SOF-based regimens, it is apparent from the number of publications of small cohort studies describing treatment of subjects with severe renal impairment with SOF-based regimens that such treatment is not uncommon {[Bhamidimarri 2015](#), [Desnoyer 2016](#), [Hundemer 2015](#), [Navarro-Millan 2013](#), [Nazario 2016](#)}. The simplicity of SOF-based dosing regimens, relative lack of drug-drug interactions, and absence of a requirement for baseline NS5A polymorphism testing or RBV use makes SOF-based regimens a viable option for physicians, even when considering the lack of dosing recommendations in this population.

The unmet medical need of the population and the ongoing off-label use of SOF-based regimens provide a strong rationale for the conduct of this study as the data obtained will address the gaps in knowledge regarding the use of SOF-based regimens in subjects with HCV infection who are on dialysis for ESRD.

1.4. Rationale for Dose Selection of LDV/SOF

Subjects in this study will be administered LDV/SOF, a co-formulation of LDV 90 mg and SOF 400 mg that is approved in the US, EU, and other regions as Harvoni® for the treatment of HCV infection in adults. The treatment durations evaluated are aligned with those outlined for RBV-free treatment in the EU prescribing information for subjects without cirrhosis or with compensated cirrhosis; specifically

- Subjects who are treatment naïve and without cirrhosis: LDV/SOF for 8 weeks
- Subjects who are treatment experienced and without cirrhosis: LDV/SOF for 12 Weeks
- Subjects who have compensated cirrhosis: LDV/SOF for 24 weeks

The results of a Phase 1 single dose study of LDV in subjects with severe renal impairment indicates that no relevant differences in LDV exposure were observed between subjects with normal renal function and subjects with severe renal impairment. In a Phase 1 study of the PK of SOF in subjects with renal impairment, the SOF and GS-331007 AUC were 171% and 451% higher, respectively, in subjects with severe renal impairment compared to subjects with normal renal function. In subjects with ESRD, SOF and GS-331007 AUC was 28-60% and 1280-2070% higher, respectively, compared to subjects with normal renal function.

Available data from the Study GS-US-334-0154 indicates that administration of SOF 400 mg with RBV 200 mg for 24 weeks in subjects with severe renal impairment was well tolerated with no specific safety signal associated with the elevated exposures of SOF or the predominant metabolite GS-331007. The exposures of SOF and GS-331007 in the GS-US-334-0154 study are consistent with the results of the Phase 1 study of SOF in subjects with severe renal impairment or ESRD. Preliminary data from the GS-US-334-0154 study suggests that the administration of LDV/SOF (90/400 mg) for 12 weeks is well tolerated and is more efficacious than administration of SOF 200 mg or 400 mg with RBV 200 mg for 24 weeks.

Based on these data, the approved dose of LDV/SOF will be evaluated in this study. Refer to the LDV/SOF IB for additional information.

1.5. Risk/Benefit Assessment for the Study

This study will provide data of the safety and efficacy of LDV/SOF in subjects with ESRD on dialysis. It is anticipated that these data will support dosing recommendations for LDV/SOF in subjects with severe renal impairment and subjects with ESRD on dialysis.

The potential benefits of LDV/SOF over the currently available treatment options are:

- LDV/SOF has broad antiviral activity against a range of HCV genotypes; it is currently approved in the US and EU for the treatment of genotypes 1, 3 (EU only), 4, 5, and 6 HCV infection. LDV/SOF may therefore provide a treatment option for a broader range of HCV infected subjects with severe renal impairment and ESRD on dialysis than the currently available treatment options which are restricted to the treatment of genotype 1 and 4 HCV infections.
- LDV/SOF will provide a highly effective and well-tolerated RBV-free treatment option for subjects on dialysis. As RBV-associated toxicities can be exacerbated in subjects with severe renal impairment, the availability of a RBV-free treatment option will enable a greater proportion of subjects with ESRD to be treated.
- The components of LDV/SOF have limited drug-drug interaction potential with medications commonly prescribed to subjects with severe renal impairment or ESRD on dialysis. This should reduce the complexity of patient management compared with the use of other antiviral treatments.

The risks associated with the evaluations of LDV/SOF in subjects with ESRD on dialysis are associated with concerns about the high exposure of the predominant SOF metabolite, GS-331007, in subjects with renal impairment and the limited data on the safety and efficacy of LDV/SOF in subjects with renal impairment. In non-clinical studies, GS-331007 exposure similar to that projected for patients with ESRD administered LDV/SOF resulted in decreased red cells counts (See Section 1.2.3).

These risks are mitigated by the following:

- Approximately 5000 subjects have been administered LDV/SOF with or without RBV to date.
- During the conduct of the study, hematologic assessments will be performed routinely and results will be reviewed by the investigator and sponsor.
- During the conduct of the study, a Data Monitoring Committee (DMC) will evaluate safety data in the study after the first n=12 subjects have completed 8 weeks of treatment, or early termination (ET), and then every 3 months until the last subject enrolled completes treatment with study drugs. Furthermore, the Sponsor and the Investigators will perform ongoing safety reviews throughout the study.

Given the medical need for a well-tolerated, highly effective, RBV-free treatment options for HCV infected subjects with ESRD on dialysis; the benefit/risk assessment of this study favors the conduct of the study.

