3.3. Duration of Treatment

Approximately 100 subjects will be enrolled to one of 3 groups and will receive treatment with LDV/SOF for 8, 12, or 24 weeks. The treatment group to which subjects are assigned will be determined by genotype, the absence or presence of cirrhosis and whether the subject is treatment naïve or treatment experienced.

Group 1: Treatment naïve genotype 1 subjects without cirrhosis will be treated with LDV/SOF for 8 weeks

Group 2: Treatment experienced genotype 1 subjects and treatment naïve or treatment experienced genotype 4, 5, and 6 subjects without cirrhosis will be treated with LDV/SOF for 12 weeks

Group 3: Subjects with compensated cirrhosis will be treated with LDV/SOF for 24 weeks

The total time to complete all study visits is up to a maximum of 52 weeks depending on the treatment duration (54 weeks for those requiring an extension of the screening period):

- 28 days (4 weeks) screening period (or 42 days for extenuating circumstances)
- 8, 12, or 24 week study treatment period
- 24 week posttreatment period

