8.10. Data Monitoring Committee

An external multidisciplinary data monitoring committee (DMC) will review the progress of the study and perform an interim review of safety data once the first 12 subjects have completed 8 weeks of treatment, or early termination. After the initial meeting, safety reviews will be conducted at approximately 3 month intervals during the trial until the last enrolled subject completes study treatment. These safety reviews will alternate between the following:

- A review by the DMC chair of all SAEs and deaths
- A review of safety data by the DMC meeting as specified in the DMC charter

The DMC will provide recommendation to Gilead on whether the nature, frequency, and severity of adverse effects associated with study treatment warrant the early termination of the study in the best interests of the participants, whether the study should continue as planned, or the study should continue with modifications. The DMC may also provide recommendations as needed regarding study design, conduct, and the need for additional meetings or an alternative meeting schedule. The DMC's specific activities will be defined by a mutually agreed charter, which will define the DMC's membership, conduct and meeting schedule.

While the DMC will be asked to advise Gilead regarding future conduct of the study, including possible early study termination, Gilead retains final decision-making authority on all aspects of the study.

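### Planned DMC reviews end when the last subject enrolled finishes treatment, which with 8-, 12- and 24-week courses can leave Group 3 subjects up to 16 weeks from finishing

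*Protocol*

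**What the plan says.** Three places fix the end of DMC review. Protocol 1.5 has reviews "every 3 months until the last subject enrolled completes treatment with study drugs". Protocol 8.10 says that "safety reviews will be conducted at approximately 3 month intervals during the trial until the last enrolled subject completes study treatment", and SAP 2.1 repeats that sentence. The three agree on the end point. (Protocol and SAP differ on when the first review falls, 8 against 12 weeks of treatment, which is a separate matter.)

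Protocol 3.3 gives three course lengths:

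- "Group 1: Treatment naïve genotype 1 subjects without cirrhosis will be treated with LDV/SOF for 8 weeks"
- The 12-week course is for Group 2: non-cirrhotic subjects who have genotype 1 and prior treatment, or genotype 4, 5 or 6 with any treatment history
- "Group 3: Subjects with compensated cirrhosis will be treated with LDV/SOF for 24 weeks"

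Allocation follows subject characteristics: "The treatment group to which subjects are assigned will be determined by genotype, the absence or presence of cirrhosis", together with treatment history. No rule governs the order in which groups enrol.

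Under Protocol 8.10 the reviews alternate between a DMC meeting and "A review by the DMC chair of all SAEs and deaths". The same section lets the DMC make recommendations on "the need for additional meetings or an alternative meeting schedule" and leaves its schedule to a charter, which is not among the documents.

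**The concern.** Tying the end of monitoring to the last subject enrolled is harmless when every course has the same length. Here the longest course is three times the shortest. A Group 3 subject who starts shortly before a final Group 1 subject will still be on drug when the planned reviews end.

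Protocol 1.5 names high exposure to the metabolite GS-331007 and limited data in renal impairment as the study's risks, and lists DMC review among the mitigations. Protocol 1.4 reports GS-331007 AUC in ESRD as 1280-2070% above that with normal renal function. The subjects who can fall outside planned external review are those with compensated cirrhosis and the longest exposure. Safety and tolerability of each regimen is also a primary objective, and the 24-week regimen is the one that loses coverage.

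**Working it through.** The documents give no figure for this gap, so there is none to reproduce. The check is calendar arithmetic.

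**Inputs.** Courses of 8, 12 and 24 weeks (Protocol 3.3). Reviews end when the last subject enrolled completes treatment (Protocol 1.5 and 8.10, SAP 2.1). The 3-month interval is taken as 13 weeks (assumption). Full courses are assumed for everyone.

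**Formula.** Weeks left on drug when reviews end = max(0, own course − course of the last subject enrolled − e), where e is the number of weeks by which the subject enrolled before the last one.

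**Upper bounds (e close to 0).**

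| Last enrolled | Reviews end, weeks after last enrolment | Group 1 left | Group 2 left | Group 3 left |
|---|---|---|---|---|
| Group 1 | 8 | 0 | 12 − 8 = 4 | 24 − 8 = 16 |
| Group 2 | 12 | 0 | 0 | 24 − 12 = 12 |
| Group 3 | 24 | 0 | 0 | 0 |

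**Earlier enrolment.** With Group 1 last, a Group 3 subject enrolled 4, 8, 12 or 16 weeks earlier has 12, 8, 4 or 0 weeks left.

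**Against the review interval.** The gap exceeds 13 weeks only with Group 1 last and a Group 3 subject enrolled less than 16 − 13 = 3 weeks before. With Group 2 last, the maximum of 12 weeks is below 13. A 16-week tail would have held 16/13 = 1.2 review intervals, so one or two reviews.

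**Timing of the last review.** The final scheduled review may itself come before the end point. For a Group 3 subject who starts on the same day as the last Group 1 subject, a final review at week 8 leaves 16 weeks of treatment unreviewed. At week 4 it leaves 20, and on or before the start it leaves all 24.

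**How many subjects (illustration only).** Assume 100 subjects enrolled evenly over A weeks, a Group 3 share s, and no early discontinuation. Group 3 subjects still on drug when reviews end = 100 × s × gap / A.

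- Group 1 last: from 100 × 0.10 × 16/52 = 3.1 to 100 × 0.30 × 16/26 = 18.5.
- Group 2 last: from 100 × 0.10 × 12/52 = 2.3 to 100 × 0.30 × 12/26 = 13.8.

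The shares (10-30%) and accrual times (26-52 weeks) are assumptions. The width of the range shows how far the count depends on them.

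**After the fix.** If reviews run until every subject is off study drug, the time left on drug is 0 weeks in all groups.

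**The case against.** The best defence is that the phrase means the last of the enrolled subjects to finish. The order of words in Protocol 8.10 and SAP 2.1 allows this, and Protocol 9.1.1 defines study completion by the last subject to complete. But Protocol 1.5 speaks of the last subject enrolled, which points to enrolment order, so this reading is strained. If it is what the sponsor meant, the wording should say so.

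The second argument is that other safeguards remain, and this stands in large part. Protocol 1.5 has the sponsor and investigators reviewing safety throughout, with routine haematology as a separate mitigation for the red-cell concern. Group 3 has haematology, chemistry and adverse-event checks at Weeks 12, 16, 20 and 24. SAEs reach the sponsor within 24 hours (Protocol 7.2.4), and individual stopping criteria apply (Protocol 3.4.1). If accrual is long enough, the DMC will already have seen full courses from earlier Group 3 subjects. What is missing is planned independent review of the late tail. Protocol 1.5 presents sponsor and investigator review as an addition to the DMC, not a replacement for it.

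The third argument is that the DMC can ask for more meetings and the charter may already cover the tail. That is fair, and it limits the point to what the two documents plan. A discretionary meeting is still not a scheduled one.

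**Conclusion.** The point holds as a gap in the planned schedule. Followed as written, planned DMC reviews can end with Group 3 subjects up to 16 weeks (Group 1 enrolled last) or up to 12 weeks (Group 2 last) from the end of treatment, and with no gap if a Group 3 subject is last. These bounds assume that the last subject enrolled takes the full course. If early discontinuation by that subject counts as completion, the gap lengthens.

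A reader might infer more than the documents support:

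- **That these subjects go unmonitored, or that the DMC will not look at them.** Sponsor and investigator review continues, extra meetings are possible, and the charter could not be checked. The supported statement is that no DMC review is planned.
- **That the gap generally exceeds the review interval.** It does so only in the Group 1 case, and only for a Group 3 subject enrolled within about 3 weeks of the last subject.
- **That a gap can be given a probability, such as 70-90%.** With random enrolment order, that figure is essentially one minus an assumed Group 3 share of 10-30%. It also counts anyone with a single day left.

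No analysis, sample size or efficacy conclusion is affected. The change is worth making because it is cheap and restores a mitigation on which the protocol relies.

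**What to change.** In Protocol 1.5, Protocol 8.10 and SAP 2.1, replace the end point with: *until all subjects have completed or permanently discontinued study treatment*. Check the DMC charter and make its schedule agree. If the charter already covers all subjects, only the protocol and SAP wording needs to change.

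The cost is one phrase in three places, a matching line in the charter, and usually one further review, two at most. No treatment rule, assessment or analysis changes.

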1.6. Compliance

This study will be conducted in compliance with this protocol, Good Clinical Practice (GCP), and all applicable regulatory requirements.

2. OBJECTIVES

The primary objectives of this study are as follows:

- To evaluate the antiviral efficacy of treatment with LDV/SOF for 8,12, or 24 weeks in subjects with chronic hepatitis C virus (HCV) infection who are on dialysis for ESRD, as measured by the proportion of subjects with sustained viral response 12 weeks after cessation of treatment (SVR12)
- To evaluate the safety and tolerability of each treatment regimen

The secondary objectives of this study are as follows:

- To determine the proportion of subjects who attain SVR at 4 and 24 weeks after cessation of each study treatment regimen (SVR4 and SVR24)
- To evaluate the proportion of subjects with virologic failure
- To evaluate the kinetics of circulating HCV RNA during treatment and after cessation of treatment
- To evaluate the emergence of viral resistance to LDV and SOF during treatment and after cessation of treatment
- To evaluate the steady-state pharmacokinetics of LDV and SOF, and its metabolites in subjects who are on dialysis for ESRD

The exploratory objectives of this study are:

CCI

3. STUDY DESIGN

3.1. Study Design

This is a multicenter, open-label Phase 2 study that will evaluate the safety, tolerability, and antiviral efficacy of LDV/SOF in subjects on dialysis for ESRD with genotype 1, 4, 5, or 6 HCV infection.

3.2. Visit Schedule

Screening assessments will be completed within 28 days of the Day 1 visit. The screening window can be extended to 42 days for extenuating circumstances with Sponsor approval.

All subjects will complete the following study visits: Screening, Day 1, on-treatment visits at the end of Weeks 2, 4, 6, and 8. Subjects in group 2 and 3 will also complete a Week 12 visit, and subjects in group 3 only, will also complete visit at Weeks 16, 20, and 24. All subjects will complete posttreatment visits at Weeks 4 and 12, after completion of treatment. Subjects who achieve SVR12 will also complete the posttreatment Week 24 visit.

3.3. Duration of Treatment

Approximately 100 subjects will be enrolled to one of 3 groups and will receive treatment with LDV/SOF for 8, 12, or 24 weeks. The treatment group to which subjects are assigned will be determined by genotype, the absence or presence of cirrhosis and whether the subject is treatment naïve or treatment experienced.

Group 1: Treatment naïve genotype 1 subjects without cirrhosis will be treated with LDV/SOF for 8 weeks

Group 2: Treatment experienced genotype 1 subjects and treatment naïve or treatment experienced genotype 4, 5, and 6 subjects without cirrhosis will be treated with LDV/SOF for 12 weeks

Group 3: Subjects with compensated cirrhosis will be treated with LDV/SOF for 24 weeks

The total time to complete all study visits is up to a maximum of 52 weeks depending on the treatment duration (54 weeks for those requiring an extension of the screening period):

- 28 days (4 weeks) screening period (or 42 days for extenuating circumstances)
- 8, 12, or 24 week study treatment period
- 24 week posttreatment period

